1.7.2 MISSING MARKERS FOR PARTICLE PROVIDERS

When marker values are not available for a plasma provider, individuals receiving plasma from that provider will be excluded from the related analysis.

1.7.3 RESULTS MISSING FOR MARKERS WHEN MEASUREMENTS ARE EXPECTED

When a marker value was expected but it is not available, multiple imputation will be used to impute the missing value based on a linear model in which imputation is carried out based on a regression model for the missing marker given the values of the available markers. When multiple markers are missing then imputation will be carried out using multiple imputation based on chained equations (White et al. 2011) with 10 imputed samples. The imputation models will be based on the joint distributions of all four markers under consideration.

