2 STATISTICAL ANALYSES INVOLVING LABORATORY DATA

As a preliminary analysis we will tabulate the availability of marker data by site, blood provider, and according to the type of the marker. A careful description of the units used to measure the markers will be carried out with any change of units carried out as required. Upon standardization of the scales the summary statistics will be computed for each marker by site, by provider, and overall. All of the analyses that follow will control for the provider as a factor variable to ensure that comparisons are made within providers. This variable is suppressed in the model statements that follow for convenience.

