2.1 REGRESSION ANALYSES INVESTIGATING ROLE OF MARKERS IN THE CCP ARM

Preliminary analyses will be directed at modeling the relations between the laboratory profile of CCP and the probability of experiencing the primary outcome. This will be done initially in a univariate fashion and then via multiple regression with several markers. Let $Y_i = 1$ if individual i is intubated or dies within 30 days and let M_{ij} be the j th marker of interest, $j = 1, \dots, J$, $i = 1, \dots, n$. Let $\pi(M_{ij}) = P(Y_i = 1|M_{ij})$ and

$$\log \left(\frac{\pi(M_{ij})}{1 - \pi(M_{ij})} \right) = \alpha_0 + \alpha_1 M_{ij},$$

be considered in the univariate analysis of marker j , $j = 1, \dots, J$, and

$$\log \left(\frac{\pi(M_i)}{1 - \pi(M_i)} \right) = \alpha_0 + \alpha_1 M_{i1} \cdots + \cdots + \alpha_J M_{iJ}$$

be considered in the multivariate analysis where $M_i = (M_{i1}, \dots, M_{iJ})'$ is the vector of markers. Tests for interactions will also be carried out to assess whether marker effects vary according to the value of other markers. Finally generalized additive models will be considered to give graphical plots of the relations between the marker values and the odds of response (Hastie and Tibshirani, 1990).

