2.2 REGRESSION ANALYSES EXPLORING THE EFFECT-MODIFYING ROLE OF EACH MARKER

The results of the antibody titre will give an indication of the amount of antibodies in the plasma transfused thereby enabling an investigation of the effect the amount of neutralizing antibodies has on the effect of CCP versus standard care. For each marker the value will be centered by subtracting the mean value among the plasma units transfused. For the primary binary response, a logistic regression model (McCullough and Nelder, 1989) will be fitted involving the treatment indicator (equalling 1 for those in the CCP arm) and an interaction between the treatment indicator and the centered marker. The coefficient of the treatment indicator will reflect the effect of CCP transfusion at the mean level of the marker, while the coefficient of the interaction term will reflect how this effect is modified according to the marker value in the transfused plasma. The details are given in what follows.

Let $Y_i = 1$ if individual i is intubated or dies within 30 days and let Z_i be their covariate vector, $i = 1, \dots, n$. Let $\pi(Z_i) = P(Y_i = 1|Z_i)$ where $Z_i' = (1, X_i, X_i M_i)$ where X_i indicates randomization to the CCP arm and M_i is the marker level in the CCP.

$$\log \left(\frac{\pi(Z_i)}{1 - \pi(Z_i)} \right) = \beta_0 + \beta_1 X_i + \beta_2 X_i M_i.$$

In order to relax the assumption of a linear effect-modifying role of the marker, generalized additive models (Hastie and Tibshirani, 1990) will be fitted for the effect of $X_i M_i$ with the results to give insight into critical threshold levels of the markers.

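### Missing donor markers are imputed without the clinical outcome, which shrinks the imputed marker's own coefficient and its interaction with treatment in the exploratory antibody models

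*SAP*

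**What the plan says.** **Imputation.** Supplement 1.7.3 covers marker values that were expected but not obtained. If one marker is missing, "imputation is carried out based on a regression model for the missing marker given the values of the available markers". If several are missing, chained equations are used "with 10 imputed samples", and "The imputation models will be based on the joint distributions of all four markers under consideration". The primary outcome, the blood provider and the patient's own markers are not named as predictors. Supplement 1.7.2 treats providers with no result for a marker separately: "individuals receiving plasma from that provider will be excluded from the related analysis".

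**Use of the imputed values.** Supplement 2.1 is directed at "modeling the relations between the laboratory profile of CCP and the probability of experiencing the primary outcome", by logistic regression in the CCP arm, first one marker at a time and then jointly. In supplement 2.2 the linear predictor is β0 + β1X + β2XM, and "the coefficient of the interaction term will reflect how this effect is modified according to the marker value in the transfused plasma". Section 2.3 extends this to several markers, and sections 2.4.1 and 2.4.2 add patient markers and product terms. Supplement section 2 states: "All of the analyses that follow will control for the provider as a factor variable".

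**Contrast.** For missing outcomes, main SAP section 4.1 does list imputation covariates, including treatment, and uses 50 imputations. The supplement has no such list for markers and plans no complete-case check of the marker models.

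**The concern.** An imputation model should contain every variable of the analysis it feeds, including the response. If the outcome is left out, each imputed marker is unrelated to the outcome given the other markers. Mixing such values with observed ones weakens the fitted association. A larger number of imputations reduces simulation noise but leaves this bias in place.

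Main SAP section 4.8 counts the effect of neutralizing antibodies among the important secondary questions and gives it as one reason for a conservative stopping rule. Section 4.6.1 sends antibody analyses to the IDSMC at the interim. A rule that weakens a marker's estimated effect could help an informative assay look uninformative.

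**Working it through.** **Inputs from the documents** (main SAP 1.1 and 1.3): 800 CCP and 400 standard-of-care patients; 30% events under standard of care; a 25% relative reduction, so 0.75 × 30% = 22.5% under CCP.

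**Assumptions, not in the documents:** 5–30% of one marker missing completely at random; equal correlation ρ of 0, 0.5 or 0.8 among four normal markers; a log odds ratio of −0.3 per SD for the incomplete marker.

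**1. The plan's own figure.** Section 1.7.3 gives no figure to recompute. The trial's sample size, whose inputs are used here, does reproduce. With a pooled rate of (0.30 + 2 × 0.225)/3 = 0.25, the standard-of-care arm needs [1.96√(0.25 × 0.75 × 1.5) + 0.8416√(0.30 × 0.70 + 0.225 × 0.775/2)]² / 0.075² = 399.1. That rounds up to 400, or 1200 in total, with power 80.1%.

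**2. Expected shrinkage, one-marker model.** Let β1 be the marker's coefficient given the other markers. A share f of values keeps only the part of the marker that the others predict. The one-marker slope therefore changes by about −f(1 − R²)β1. If the other markers have no effect of their own, the slope becomes 1 − f(1 − R²) of its true value. For four equally correlated markers R² = 3ρ²/(1 + 2ρ), which is 0, 0.375 and 0.738 for ρ = 0, 0.5 and 0.8.

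**3. Simulation.** 300 runs per cell, linear multiple imputation with m = 10, Rubin's rules. Entries are the mean estimate as a fraction of truth, with the formula in brackets.

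| Missing | ρ = 0 | ρ = 0.5 | ρ = 0.8 |
|---|---|---|---|
| 5% | 0.97 (0.95) | 0.97 (0.97) | 0.99 (0.99) |
| 10% | 0.90 (0.90) | 0.96 (0.94) | 0.98 (0.97) |
| 20% | 0.83 (0.80) | 0.86 (0.88) | 0.96 (0.95) |
| 30% | 0.70 (0.70) | 0.81 (0.81) | 0.91 (0.92) |

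With the outcome added to the imputation model, every cell lies between 0.98 and 1.04. Full-data estimates lie between 0.99 and 1.03, and complete-case estimates between 0.98 and 1.04. At 30% missing, power for the marker effect is 57%, 76% and 88% without the outcome, against 81%, 89% and 91% with it (about 94% with full data).

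**4. Effect modification.** In the model printed in supplement 2.2 the marker enters only in the CCP arm, so β2 equals the CCP-arm slope. The two agreed to within rounding error in every cell. The interaction therefore shrinks by the same factor. The printed model suppresses the provider term, and the check did too.

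**5. Multi-marker models.** With two markers, only the first incomplete, its joint coefficient should become about (1 − f)β1, and the observed marker's should move by about fρβ1. One large simulated dataset (n = 1,000,000) at 30% missing gave:

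- Both effects −0.3, ρ = 0.5: the incomplete marker went from −0.296 to −0.207. The observed one went from −0.303 to −0.345 (expected shift 0.3 × 0.5 × −0.3 = −0.045).
- Both effects −0.3, ρ = 0.8: −0.297 to −0.203, and −0.304 to −0.377 (expected shift −0.072).
- Observed marker with no effect, ρ = 0.8: its coefficient moved from −0.003 to −0.074.

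In the joint model the incomplete marker thus loses about the full fraction f, whatever the correlation, and the observed marker absorbs part of the loss.

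**6. Opposing effects.** With effects of −0.3 and +0.4, ρ = 0.8 and 30% missing, the one-marker slope moved from 0.020 to 0.051, away from zero. Step 2 predicts 0.020 + 0.3 × 0.36 × 0.3 = 0.052. If β1 = 0, no bias is expected; the simulated one-marker slope for ρ = 0.8 stayed at −0.238.

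**7. Size against precision.** The slope's standard error with 800 CCP patients is about 1/√(800 × 0.225 × 0.775) = 0.085 per SD. The bias is 0.05 × 0.625 × 0.3 = 0.009 (0.11 SE) at 5% missing and ρ = 0.5, and 0.30 × 0.3 = 0.09 (about 1.1 SE) at 30% missing and ρ = 0.

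**The case against.** **The bias may be negligible.** Main SAP 4.6.1 plans antibody testing for all transfused units, protocol section 5.6 plans neutralization results for all samples, and supplement 1.7.2 excludes providers without a marker. Only sporadic gaps may be left. This stands: at 5% missing the one-marker loss is a few percent at most. The documents do not give the fraction, however; they say only that "we will tabulate the availability of marker data by site, blood provider, and according to the type of the marker". A patient with no marker at all has R² = 0, so that share is lost in full.

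**The bias always runs towards no effect.** A reader might infer this, and it does not hold. It describes the imputed marker's own coefficient in the usual case. Under the joint models of 2.1 and 2.3 a correlated observed marker can be inflated, or an inert one can appear active. Opposing effects can reverse the direction even in a one-marker model.

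**The outcome is not expressly excluded.** True, but both imputation cases name only markers as the basis, and an analyst following the text would build a markers-only model.

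**The analyses are exploratory.** True. The primary test, sample size and interim boundary do not use marker imputation. A reader who inferred a threat to the main result would be wrong.

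**Adding the outcome is not a one-line change.** This stands. Section 1.7.3 does not say whether imputation is per unit or per patient, or on the raw or log scale. One donation can fill two or three bags (protocol 5.4.2.1) and so could reach patients with different outcomes, which leaves outcome-based imputation per unit undefined without further rules.

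**Conclusion.** The point holds for the imputed marker's own coefficient. Followed as written, section 1.7.3 shrinks that coefficient, and the matching interaction in section 2.2, by roughly f(1 − R²) in one-marker models. That is about 0–5% at 5% missing and up to about 30% at 30% missing when the other markers are uninformative. Both f and R² are assumptions, as is the simulated slope of −0.3, and the formula supposes that the other markers have no effect of their own. In joint models the loss is nearer f, and part of the effect can shift to correlated markers. The documents therefore support neither a general bias towards no effect nor a claim that the loss is large in this trial. If values are missing at random with respect to everything, dropping incomplete cases would be less biased than the planned imputation. The primary analysis is unaffected. The change is worth making because the plan itself gives the antibody question weight.

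**What to change.** Amend supplement 1.7.3 as follows:

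- Impute at patient level within the CCP arm, after units are combined by volume, on the log10 scale used for analysis. State how a patient with only one of two units measured is handled.
- Include the primary outcome and the blood provider, which is already in every analysis model, in each marker imputation equation, whether one or several markers are missing.
- For sections 2.4.1 and 2.4.2, also include the patient markers and the relevant product terms.
- State the number of imputations for both cases.
- Report a complete-case analysis as a sensitivity check, with the missing fraction for each marker.

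The cost is a short paragraph and some programming, with no new data. One limitation remains: imputation that is linear in the outcome only approximates the planned additive models and marker interactions, so results from those models should be read with that in mind.

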2 STATISTICAL ANALYSES INVOLVING LABORATORY DATA

As a preliminary analysis we will tabulate the availability of marker data by site, blood provider, and according to the type of the marker. A careful description of the units used to measure the markers will be carried out with any change of units carried out as required. Upon standardization of the scales the summary statistics will be computed for each marker by site, by provider, and overall. All of the analyses that follow will control for the provider as a factor variable to ensure that comparisons are made within providers. This variable is suppressed in the model statements that follow for convenience.

2.1 REGRESSION ANALYSES INVESTIGATING ROLE OF MARKERS IN THE CCP ARM

Preliminary analyses will be directed at modeling the relations between the laboratory profile of CCP and the probability of experiencing the primary outcome. This will be done initially in a univariate fashion and then via multiple regression with several markers. Let $Y_i = 1$ if individual i is intubated or dies within 30 days and let M_{ij} be the j th marker of interest, $j = 1, \dots, J$, $i = 1, \dots, n$. Let $\pi(M_{ij}) = P(Y_i = 1|M_{ij})$ and

$$\log \left(\frac{\pi(M_{ij})}{1 - \pi(M_{ij})} \right) = \alpha_0 + \alpha_1 M_{ij},$$

be considered in the univariate analysis of marker j , $j = 1, \dots, J$, and

$$\log \left(\frac{\pi(M_i)}{1 - \pi(M_i)} \right) = \alpha_0 + \alpha_1 M_{i1} \cdots + \cdots + \alpha_J M_{iJ}$$

be considered in the multivariate analysis where $M_i = (M_{i1}, \dots, M_{iJ})'$ is the vector of markers. Tests for interactions will also be carried out to assess whether marker effects vary according to the value of other markers. Finally generalized additive models will be considered to give graphical plots of the relations between the marker values and the odds of response (Hastie and Tibshirani, 1990).

2.2 REGRESSION ANALYSES EXPLORING THE EFFECT-MODIFYING ROLE OF EACH MARKER

The results of the antibody titre will give an indication of the amount of antibodies in the plasma transfused thereby enabling an investigation of the effect the amount of neutralizing antibodies has on the effect of CCP versus standard care. For each marker the value will be centered by subtracting the mean value among the plasma units transfused. For the primary binary response, a logistic regression model (McCullough and Nelder, 1989) will be fitted involving the treatment indicator (equalling 1 for those in the CCP arm) and an interaction between the treatment indicator and the centered marker. The coefficient of the treatment indicator will reflect the effect of CCP transfusion at the mean level of the marker, while the coefficient of the interaction term will reflect how this effect is modified according to the marker value in the transfused plasma. The details are given in what follows.

Let $Y_i = 1$ if individual i is intubated or dies within 30 days and let Z_i be their covariate vector, $i = 1, \dots, n$. Let $\pi(Z_i) = P(Y_i = 1|Z_i)$ where $Z_i' = (1, X_i, X_i M_i)$ where X_i indicates randomization to the CCP arm and M_i is the marker level in the CCP.

$$\log \left(\frac{\pi(Z_i)}{1 - \pi(Z_i)} \right) = \beta_0 + \beta_1 X_i + \beta_2 X_i M_i.$$

In order to relax the assumption of a linear effect-modifying role of the marker, generalized additive models (Hastie and Tibshirani, 1990) will be fitted for the effect of $X_i M_i$ with the results to give insight into critical threshold levels of the markers.

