12. STATISTICAL CONSIDERATIONS

12.1. Sample Size Considerations

Assuming a baseline risk of intubation or death by Day 30 of 30% in hospitalized patients with standard of care, a sample size of 1200 (800 in the CCP arm, and 400 in the standard of care arm) would provide 80% power to detect a relative risk reduction of 25% with CCP therapy using a 2-tailed test at level α = 0.05. This assumes no patient is lost to follow-up. Lost follow-up is expected to be minimal.

There is uncertainty about the intubation and mortality rate that will be observed in this study due to possibly evolving profile of COVID-19 patients admitted hospital over the course of the pandemic. To address this, a blinded sample-size re-estimation will take place when the primary outcome is available for 50% of the target sample. Sample size will only be adjusted if the estimated event rate is different than the originally specified event rate to a sufficient extent that the study is not expected to achieve the desired nominal power for the test of the primary outcome.

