1.3. Sample Size Justification

Assuming a 30% risk of the composite outcome of intubation or death by Day 30 among hospitalized patients under standard of care, a sample size of 1200 individuals (800 in the CCP arm, and 400 in the standard of care arm) will provide 80% power ($\beta = 0.20$) to detect a relative risk reduction of 25% with CCP therapy using a 2-tailed test at level $\alpha = 0.05$. We assume that no patient will be lost to follow-up.

2. Responses

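### The exploratory marker models compare non-randomised plasma and adjust only for provider, so a calendar trend shared by patient risk and plasma titre could be misread as effect modification

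*SAP*

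**What the plan says.** Supplement 2.2 models the log odds of intubation or death within 30 days as β0 + β1·X + β2·X·M. X indicates randomisation to CCP and M is the centred marker level of the transfused plasma. Of β2 it says that "the coefficient of the interaction term will reflect how this effect is modified according to the marker value in the transfused plasma". Supplement 2.3 extends this to several markers, and Supplement 2.1 fits marker slopes in the CCP arm alone.

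On adjustment, Supplement 2 says: "All of the analyses that follow will control for the provider as a factor variable to ensure that comparisons are made within providers". Sections 2.1–2.3 name no other adjuster. Section 2.4 brings in the patient's own marker, but to ask a further question about effect modification rather than to control confounding.

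On allocation, Protocol 4.3 randomises the arm, stratified by centre and age. Protocol 4.1.1 and 4.2 tie the plasma to ABO compatibility and to what is available when eligibility is assessed.

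On time, Protocol 12.1 justifies blinded sample size re-estimation by a "possibly evolving profile of COVID-19 patients admitted hospital over the course of the pandemic"; SAP 4.10 says the same. No section states a trend in titre. Supplement 1.3 does record that PRNT50 was capped at 1:1280 for some samples tested early in the pandemic and at 1:640 otherwise.

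**The concern.** X·M is zero for every control, so the control arm carries no information on how outcome varies with the marker. β2 rests on differences between CCP recipients who happened to receive different plasma. The provider factor removes differences between suppliers, including those caused by countries joining at different times. It does not touch a trend within one supplier. If later patients of that supplier had lower risk and also received higher-titre plasma, β2 would show an apparent potency effect. If titre moved the other way, a real effect could be hidden.

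The analysis is exploratory, but its results may be used. SAP 4.8 lists the effect of neutralising antibodies among the important secondary questions. Supplement 2.2 hopes to find threshold levels, and Supplement 2.3 to identify particularly effective plasma. SAP 4.6.1 sends antibody analyses to the IDSMC at the interim. Neither the SAP nor the supplement tells the reader that the marker contrast is observational.

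**Working it through.** **The plan's own figure.** SAP 1.3 has "1200 individuals (800 in the CCP arm, and 400 in the standard of care arm"; 30% under standard of care, a 25% relative reduction (to 22.5%), two-sided 0.05, 80% power. With pooled risk (0.30 + 2 × 0.225)/3 = 0.25, the control arm needs [1.960·√(0.25 × 0.75 × 1.5) + 0.842·√(0.30 × 0.70 + 0.225 × 0.775/2)]² / 0.075² = (1.039 + 0.459)² / 0.005625 ≈ 399. Rounded up to 400, that is 1200 in total, with power 80.1%. The figure reproduces. The documents give no figure for the marker models.

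**What β2 estimates.** Without the provider term, β2 from the two-arm model and the slope from the CCP-only model are the same number. A test fit on simulated data gave −0.01712 from both.

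**Size if both drifts occur.** Assumptions, none of them from the documents:
- no CCP effect and no marker effect;
- marker SD 0.35 log10 at any given time;
- risk falling from 35% to 25%, so Δ = logit(0.25) − logit(0.35) = −0.480;
- mean titre rising by δ = 0.15, 0.30 or 0.45 log10.

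In large samples, to a good approximation, spurious β2 = (δΔ/k) / (0.35² + δ²/k). Here k = 12 for linear drift across accrual and k = 4 for one step between two equal halves. With 800 CCP patients and about 30% events, SE ≈ 1/√[800 × 0.3 × 0.7 × (0.35² + δ²/k)].

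| Drift | δ | β2 | OR per log10 | SE | Rejection by formula | Rejection simulated with provider factor |
|---|---|---|---|---|---|---|
| linear | 0.15 | −0.048 | 0.95 | 0.219 | 6% | 6% |
| linear | 0.30 | −0.092 | 0.91 | 0.214 | 7% | 7% |
| linear | 0.45 | −0.129 | 0.88 | 0.207 | 10% | 10% |
| step | 0.15 | −0.140 | 0.87 | 0.216 | 10% | 9% |
| step | 0.30 | −0.248 | 0.78 | 0.203 | 23% | 20% |
| step | 0.45 | −0.312 | 0.73 | 0.185 | 39% | 37% |

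One log10 is 1/0.35 ≈ 2.9 marker SDs. Per SD, the largest step bias is exp(−0.312 × 0.35) ≈ 0.90.

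**One drift only.** If δ = 0 or Δ = 0 the numerator vanishes. Simulated rejection is then about 5%.

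**Direction.** Reversing the sign of δ reverses the bias. In a separate simulation with four providers and linear drift, a within-provider marker–time correlation of −0.2 gave an OR per SD of 1.02 when risk fell from 35% to 25%, and 1.09 when it fell from 45% to 15%.

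**Wider assumptions.** In that simulation, correlations of 0.2, 0.4 and 0.6 gave rejection of 5%, 10% and 18% for risk 35% to 25%. For the extreme 45% to 15% they gave 17%, 49% and 84%.

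**With calendar time added as a main effect.** OR per SD about 1.00, and rejection 4–6% in every scenario.

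**The case against.** A reader might infer that pandemic drift will appear as a change in CCP benefit. The documents do not support that. Bias needs drift in both risk and titre, correlated within provider. The protocol calls patient drift only possible and gives neither size nor direction. The evidence for titre drift is thin. Protocol 5.4.1.1 says only that donor criteria may change, and Protocol 5.4.2.1 has titre monitored at each donation. The one documented time feature, the higher early PRNT50 ceiling, concerns one of four markers. It could lower the recorded value of the same high-titre plasma by log10(1280/640) = 0.30 over time, which is opposite to the rise simulated above. The larger rejection rates also depend on an abrupt step; linear drift between the same endpoints gives at most about 10%. All of this stands, and it makes the point conditional.

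It is also fair that the analysis is labelled exploratory (SAP 4.6, Protocol 12.4.5) and that Protocol 2.2 and 12.4.5 speak of association. SAP 4.6.1 openly notes that titre main effects are absent, and the provider factor shows that the authors had comparability in mind. That lowers the stakes. It does not close the gap: Supplement 2.2 still reads β2 as modification of the CCP effect, and within-provider time trends remain uncontrolled.

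**Conclusion.** The point holds in conditional form. Three things are certain from the documents: the marker level is not randomised, β2 is identified only among CCP recipients, and Supplement 2.1–2.3 adjust for provider alone. It follows that calendar trends in risk and titre shared within a provider would bias β2 and the CCP-arm slopes, in either direction. Whether this happens, and how strongly, cannot be known from the plan. For the assumed fall in risk from 35% to 25% and titre rise of 0.15–0.45 log10, false-positive rates run from about 6–10% (linear) to 9–37% (step), against about 5% if either drift is absent. The change is worth making because it is cheap and these models are meant to inform plasma selection. The randomised primary comparison is not affected.

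**What to change.** In Supplement section 2, extend the adjustment so that all marker models include, besides provider, calendar time of randomisation (period or spline) as a main effect. In the two-arm models it applies to patients in both arms, so that controls help to estimate the time trend. Age group and recipient ABO group are already collected and may be added as prognostic or allocation covariates, but no calculation here shows that they are needed.

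Add a sentence that β2 and the CCP-arm slopes are observational associations. Adjusting for time does not turn them into randomised contrasts. Nor does it harmonise the two PRNT50 ceilings, which is a separate coding decision.

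The cost is wording in the supplement, a few degrees of freedom and a slightly wider confidence interval for β2. No new data are needed.
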